9.2.2 Assessment of the Relationship of Adverse Events to Study Drug

The Investigator will make a causality assessment about the relationship of each AE to study drug. To ensure consistency of AE and SAE causality assessments, Investigators should apply the following general guideline:

Not Related: The AE has an etiology other than the study drug (e.g., preexisting medical condition, underlying disease, intercurrent illness, or concomitant medication); and/or the AE has no plausible temporal relationship to administration of the study drug (e.g., cancer diagnosed 2 days after dose of study drug).

Related: An AE that is related to the study drug or its administration (i.e., an event that follows a reasonable temporal sequence from administration of the study intervention, follows a known or expected response pattern to the suspected intervention, that could not be reasonably explained by the known characteristics of the subject's clinical state).

For all AEs and SAEs, Investigators will make separate assessments of causality about the relationship of the event to study drug and to study procedures (i.e., IVT injection).

Note: The Investigator's assessment of causality for individual AE reports is part of the study documentation process and will be recorded in the subject's medical record, AE eCRF, or paper AESI/SAE/Special Situation form if applicable. Adverse events recorded without the Investigator's assessment of the relationship to study drug will be followed up until causality is assigned.

9.2.3 **Assessment of the Outcome of Adverse Events**

The Investigator will record the outcome of AEs and SAEs using the following criteria:

- **Recovered/resolved:** The subject has fully recovered from the event, with no residual effects observable.
- Recovered/resolved with sequelae: The subject has recovered from the event, but with residual sequelae effects observable.
- Not recovered/resolved: Effects of the event are still present.
- **Recovering/resolving:** The subject has improved but has not fully recovered from the event.
- **Fatal:** The death is related to the event.
- Unknown: The outcome of the event is unknown to the reporter (eg, subject was lost to follow-up).

ProQR Therapeutics Page 42 of 65

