6.1.2 Placebo

for additional details.

No placebo is used.

6.1.3 **Study Drug Shipment and Storage**

Please refer to the Pharmacy Manual and Study Reference Manual for details on shipment, storage, handling, preparation, and administration.

6.1.4 **Study Drug Accountability and Reconciliation**

The Investigator must designate a research pharmacist or other staff member to maintain an inventory record of drugs received and dispensed. Additional details on study drug handling are provided in the Pharmacy Manual and the Study Reference Manual.

6.1.5 **Dosage and Administration**

The study eye is the study/treatment eye as defined in the preceding QR-421a study; the fellow eye is the fellow/contralateral eye as defined in the preceding QR-421a study. In general, QR-421a will be administered as a 180 µg loading dose on day 1, followed by 60 µg maintenance doses at 6-month intervals. Modifications for individual participants, defined based on the dosing and/or timing of their participation completion in the previous QR-421a study are outlined below

ProQR Therapeutics Page 30 of 65

Investigational Product: QR-421a Protocol No. PQ-421a-002 (Version 4)

ProQR Therapeutics Page 31 of 65 24 May 2022

Investigational Product: QR-421a Protocol No. PQ-421a-002 (Version 4)

ProQR Therapeutics Page 32 of 65 24 May 2022

QR-421a will be administered via IVT injection in accordance with the procedures outlined by the American Academy of Ophthalmology (Avery 2014). The pharmacist (or other personnel qualified to prepare study drug for administration) at each study center will receive study drug and will prepare and/or dilute the study drug with sterile solvent (PBS) when necessary, according to the Pharmacy Manual for each administration.

Administration of study drug will only be performed by qualified ophthalmologists in an inclinic setting. No other medications should be mixed with study drug. Reference is made to the Pharmacy Manual and Study Reference Manual for detailed instructions on the IVT injection.

6.2 **Concomitant Medications and Auxiliary Therapy**

6.2.1 **Prohibited Concomitant Medications**

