In order to be qualified as a suspected unexpected serious adverse reaction (SUSAR), the AE must meet 3 criteria: the event is serious, there is a certain degree of probability that the event is a reaction to the study drug being researched and the nature and severity of the reaction are not in agreement with the product information (i.e., the reaction is unexpected as per the reference safety information). All SUSARs will be reported as required to the Competent Authorities and to the Ethics Committee (EC)/Institutional Review Boards (IRBs) of the countries and centers concerned.

ProQR Therapeutics Page 40 of 65

9.1.4 **Adverse Events of Special Interest**

9.2 **Assessment of Adverse Events**

The Investigator is responsible for assessing the seriousness, severity and causality of AEs.

9.2.1 **Assessment of Severity (Intensity) of Adverse Events**

On the AE eCRF, the Investigator will use the adjectives MILD, MODERATE, or SEVERE to describe the maximum intensity of the AE. For purposes of consistency, these intensity grades are defined as follows:

- MILD: Does not interfere with subject's usual function.
- MODERATE: Interferes to some extent with subject's usual function.
- SEVERE: Interferes significantly with subject's usual function.

As described previously in Section 9.1.2, note the distinction between the severity and the seriousness of an AE. A severe event is not necessarily a serious event and may not meet the regulatory definition of serious. For example, a headache may be severe (interferes significantly with subject's usual function) but would not be classified as a serious AE unless it met one of the regulatory criteria for SAEs, listed above in Section 9.1.2.

ProQR Therapeutics Page 41 of 65 Any change in severity should be noted in the eCRF, e.g., a change from mild to severe or a change from severe to moderate should be noted with the start and stop dates for each intensity.

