10.6 Subject Disposition, Demographics and Baseline Disease Characteristics

Subject disposition, baseline demographics and disease characteristics will be summarized for all subjects combined, and potentially grouped by baseline characteristics. Such grouping of subject disposition, demographics and disease characteristics by baseline characteristics will be described in the SAP.

10.7 **Treatment Compliance**

All doses are observed and administered by study staff. Treatment compliance will be determined by source records documenting treatment observations and summarized.

10.8 **Safety Analyses**

10.8.1 **Treatment Emergent Adverse Events**

A treatment-emergent AE (TEAE) is defined as an event that was not present prior to administration of the dose of study drug and present after the dose or if it represents the exacerbation of an event that was present prior to the dose.

Adverse events noted during the study will be coded to system organ classes (SOCs) and preferred terms (PTs) using the Medical Dictionary for Regulatory Activities (MedDRA) dictionary.

ProQR Therapeutics Page 48 of 65 The overall incidence of TEAEs will be classified by SOC and PT, and potentially summarized by groups based on baseline characteristics. Deaths, AE severity, seriousness, relationship to study drug will also be tabulated, potentially by groups based on baseline characteristics. If included, grouping based on baseline characteristics will be described in the SAP.

Ocular AEs will be presented separately for the study eye and the fellow eye.

10.8.2 **Other Safety Assessments**

Ophthalmology findings will also be summarized using descriptive statistics, frequencies, and percentages, and shifts from baseline, as appropriate. The number of subjects with a 10- and 15-letter decrease from baseline in BCVA will be tabulated.

10.9 **Systemic Exposure Analyses**

Systemic exposure will be estimated using standard methodology, if adequate serum concentrations of QR-421a are detected.

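### Protocol 9.2.2 lets an event caused only by the injection be coded either related or not related to study drug, although drug and injection causality are to be judged separately

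*Protocol*

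**What the plan says.** The heading of Protocol 9.2.2 and its opening sentence confine the scale to the drug: "The Investigator will make a causality assessment about the relationship of each AE to study drug". Two categories follow.

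- 'Related' begins "An AE that is related to the study drug or its administration". The explanation after it speaks of the study intervention and the suspected intervention, not of the drug.
- 'Not Related' begins "The AE has an etiology other than the study drug". Its examples are other illnesses and concomitant medication; the injection is not mentioned.

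The next paragraph applies to every event, serious or not: "Investigators will make separate assessments of causality about the relationship of the event to study drug and to study procedures (i.e., IVT injection").

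Protocol 6.1.5 fixes what administration means here: "QR-421a will be administered via IVT injection". In the analysis, Protocol 10.8.1 states: "Deaths, AE severity, seriousness, relationship to study drug will also be tabulated". Relationship to the procedure is not in that list. Section 4.2.2.1 asks that drug-related events be weighed in the benefit-risk assessment, and 9.4 requires immediate telephone notification of fatal or life-threatening events that the investigator attributes to the drug.

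**The concern.** The act that is to be judged separately is also part of the definition used for the drug judgement. The drug field then has no single meaning: one site may mark an injection-site haemorrhage as drug-related because the injection is how the drug was administered, while another may mark it not related because the drug itself did not cause it. Both would be following the text.

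At stake is the reading of the primary endpoints, the incidence and severity of ocular and non-ocular AEs. Every injected eye receives drug and procedure together, and there is no sham or placebo arm in this study. Section 2.3 itself lists the risks of oligonucleotides and the risks of the injection procedure as different things. A drug-related count that mixes the two in an unknown proportion cannot be read as either.

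**Working it through.** No figure in the plan is involved, so there is nothing to reproduce. The check takes one test case, an event caused only by the injection, through each rule in 9.2.2.

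| Rule | Test | Result for the test case |
|---|---|---|
| 'Related' | Related to the drug or to its administration? | Met: administration is the injection (6.1.5) |
| Explanation of 'Related' | Plausible timing after the intervention, recognised response to it, not explained by the subject's condition? | Can be met: an injection complication satisfies all three |
| 'Not Related', first limb | Cause other than the drug? | Met |
| Separate-assessment paragraph | Drug and injection judged apart? | Drug no, injection yes |

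The two categories should exclude each other, yet the first three rows place the same event in both. Only the last row gives a single answer, and it conflicts with the first.

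Next, whether the procedure field can undo the mixing. Write the two answers as (drug, procedure).

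- Drug only: (yes, no).
- Drug and injection both: (yes, yes).
- Injection only, coded from 'Not Related': (no, yes).
- Injection only, coded from 'Related': (yes, yes).

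The second and fourth lines carry the same pair of answers. The procedure field therefore identifies which events are in doubt, but cannot say which of them involved any suspicion of the drug.

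For the size, let D be the number of events with genuine suspicion of the drug, P the number caused only by the injection, and c the share of P coded as drug-related. Assuming D is otherwise coded correctly, the reported drug-related count is D + cP with 0 ≤ c ≤ 1, so it lies between D and D + P. The documents give none of D, P or c.

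Finally, other places that might settle the meaning. Section 9.1.3 requires that "there is a certain degree of probability that the event is a reaction to the study drug being researched", which does not mention administration and so is narrower than 'Related' in 9.2.2. SAP 5.6 gives no rule for separating drug-related from injection-related events. No text in the two documents resolves the conflict.

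**The case against.** The strongest reply is that the wording is only a general guideline, that one scale may be meant to serve both judgements, and that the separate-assessment paragraph shows the intent. The intent is indeed visible. But the heading and the opening sentence tie the scale to the drug, and no definition for the procedure is given, so the reply does not remove the overlap. Case report form completion guidelines exist (Protocol 7.1) and might settle it; they are not part of these documents.

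Several stronger readings are tempting and are not supported.

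- A reader might infer that sites are obliged to mark injection events as drug-related, so that the drug-related count contains all of them. 'Not Related' fits those events equally well, so coding is ambiguous rather than forced.
- A reader might infer that the mixed category is what will be reported. Protocol 10.8.1 plans that tabulation, but SAP section 6 cuts the output back after the early stop, SAP 5.6 names no table by relationship, and the shells are in a separate document (SAP section 8).
- A reader might take investigator causality as the sole means of separating drug from injection effects. SAP 5.6 also reports ocular AEs by eye and time to onset from the last dose in that eye, and Protocol 7.2 staggers the eyes. These help, without replacing the causality judgement.
- A reader might use the number of injections as the size. Under Protocol 7.2, before Month 24 the fellow eye has 4 (Months 0, 6, 12, 18) and the study eye 4 (from Month 3) or 3 (from Month 9), so 8 or 7 per subject. That counts planned opportunities, assumes both eyes are dosed for the full anticipated 24 months, and ignores the early stop. It is not a count of errors.
- A reader might see a safety signal being missed, or the SUSAR rule distorted. Section 9.1.3 has its own criterion and also requires unexpectedness, and an over-inclusive 'Related' errs towards reporting more.

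It is also fair that the SAP is a close-out plan, so rewording the protocol cannot alter judgements already recorded.

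**Conclusion.** The inconsistency is real and worth correcting. Section 9.2.2 gives two incompatible answers for an event caused only by the injection, and the field concerned feeds the planned tabulation in 10.8.1, the benefit-risk input in 4.2.2.1 and the notification rule in 9.4. The result is possible inconsistent coding between sites and, where the 'Related' wording is followed, injection-only events in the drug-related count.

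The effect on that count is bounded but not estimated. It matters most for ocular events, where injection complications would be expected. The study is descriptive and has been stopped early, which limits the practical consequence; it does not make an ambiguous drug-related count interpretable. The conclusion assumes that no document outside these two gives sites a clearer rule.

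**What to change.** In the study-drug definition in Protocol 9.2.2 (or in completion guidelines, and in any later protocol built on this text):

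1. Delete the words 'or its administration' from 'Related', and replace both mentions of an intervention in its explanation with the study drug.
2. State under 'Not Related' that an event explained only by the IVT injection is not related to study drug.
3. Give relationship to the IVT procedure its own definition.

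For data already collected, query the events marked related to both drug and procedure and ask whether the drug itself was suspected. Events marked related to procedure but not to drug are already separated. In the SAP 5.6 AE overviews and the SAP 5.7 AE listings, show drug-related and procedure-related events separately, and state in the study report which definition applied.

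The cost is a few sentences of text, a small number of causality queries, and an extra row in the overviews. Answers to queries given after the event may be less reliable than the judgement at the time, so the report should keep both the recorded and the queried answer.

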To address the potential risks defined in the toxicology studies, the reported risks from oligonucleotides administered by IVT injection, and the risks associated with the IVT injection procedure, extensive monitoring to protect subject safety is incorporated in this study and will include assessments of subjects' ophthalmic function and anatomy, in particular, monitoring of anterior, intermediate and posterior segment inflammation by slit-lamp biomicroscopy, clinical lens grading using the Age-Related Eye Diseases Study (AREDS) Clinical Lens Grading

ProQR Therapeutics Page 19 of 65 System, monitoring for retinal changes by OCT, and VF testing to monitor changes in retinal sensitivity. This extensive clinical monitoring provides a means to allow early detection and/or prevention of potential AEs such as early signs of macular edema appearance or worsening, decrease in BCVA, the elevation of IOP, intraocular inflammation, lens opacities, and retinal structural modifications. In addition, the visit schedule is designed to monitor subjects one day following IVT injection and a second time within 1 week of IVT injection to monitor for signs of endophthalmitis and intraocular inflammation, consistent with guidelines for IVT injections (Avery 2014).

ProQR Therapeutics Page 20 of 65 24 May 2022

Detailed information about benefits and potential risks of QR-421a, as well as information on nucleotide AONs as a class of therapeutics can be found in the IB.

2.4 **Study Rationale**

There are currently no approved therapies for the treatment of RP due to mutations in exon 13 of the USH2A gene and disease management is supportive; therefore, an important unmet medical need exists in this condition.

Available safety and efficacy data from study PQ-421a-001 support the therapeutic potential observed in the nonclinical studies and warrant the initiation of the additional clinical studies to confirm benefit-risk.

This extension study allows subjects having participated in QR-421a clinical studies, including study PQ-421a-001, to continue to receive treatment, or follow up, and to observe the long-term safety, tolerability, systemic exposure, and efficacy of treatment with QR-421a. Additionally, this extension study allows for the treatment of the previously untreated fellow/contralateral eye for subjects from study PO-421a-001.

2.5 **Dose Selection**

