9.4 Serious Adverse Events Notification

For all SAEs, regardless of suspected causality, a completed AESI/SAE/Special Situation form must be sent within 24 hours of discovery of the event to:

DRUG SAFETY

See Study Reference Manual

Any fatal or life-threatening (ie, imminent risk of death) event that is attributed by the Investigator to the study drug must be immediately telephoned to:

DRUG SAFETY

Phone: See Study Reference Manual for phone number

followed by submission of written case details on an AESI/SAE/Special Situation form within 24 hours.

Serious AEs occurring any time after study participation that are considered by the Investigator to be possibly related to study drug must also be reported. The following are important points to remember when completing the AESI/SAE/Special Situation form:

- If complete information is not available, at a minimum, subject identifier, suspect drug, study center identifier, event or outcome, and Investigator assessment of causal relationship to study drug should be provided.
- A rationale for the causality assessment of an SAE should always be included, so that a better understanding of the event can be compiled.
- Follow-up information, such as laboratory reports, discharge summaries, autopsy reports, and information concerning outcome of the event should be submitted by revising the AESI/SAE/Special Situation form as soon as the information becomes available. Copies of source documents, with subject identifiers redacted, should be submitted only when they are written in English. If source documents are not in English, the Investigator must summarize the source documents, providing a complete English narrative that includes a description of the events as it evolved, the results of all diagnostic procedures performed, treatments administered, and outcome of the event. A query regarding a follow-up report should be answered within 5 working days from receipt of the query.
- Appropriate diagnostic tests and therapeutic measures are to be performed as necessary and reported on the AESI/SAE/Special Situation form.

ProQR Therapeutics Page 46 of 65 24 May 2022

All SAEs must be reported to the IRB/EC, if applicable. See the International Council for Harmonisation (ICH) GCP E6 (R2), Section 4.11.1 (ICH 2016).

9.5 **Expedited Reporting of Suspected Unexpected Serious Adverse Reactions**

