10.0 STATISTICAL METHODOLOGY

10.1 **General Considerations**

A comprehensive Statistical Analysis Plan (SAP) will specify the statistical methodology, including interim data reviews (if conducted) and table, listing, and figure (TLF) formats for all aspects of the planned analyses. The SAP supports the completion of the Clinical Study Report (CSR) for this protocol.

All AEs will be considered in determining the safety profile of QR-421a. As an early phase clinical study, exploratory analyses not necessarily identified in the SAP may be performed to support the clinical development program. Any p values that will be calculated according to the analysis plan will be interpreted in view of the exploratory nature of the study. Any post hoc, or unplanned, analyses not identified in the SAP will be clearly identified in the CSR, in accordance with applicable Standard Operating Procedures of the sponsor.

10.2 **Determination of Sample Size**

The sample size is determined by the number of subjects completing preceding QR-421a studies, including PQ-421a-001, who meet the inclusion and exclusion criteria and provide informed consent.

10.3 **Randomization and Masking**

This is an open-label study; randomization and masking are not required.

ProQR Therapeutics 24 May 2022

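### As written, the definition of Related in Protocol 9.2.2 leaves novel reactions without a category and steers events the disease could also explain to Not Related

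*Protocol*

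**What the plan says.** Protocol 9.2.2 allows two answers for the relationship of an adverse event to study drug.

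- **Related** is explained by a bracket opening with 'i.e.' that describes "an event that follows a reasonable temporal sequence from administration of the study intervention". It then adds two conditions, the second of which concerns the subject's clinical state: the event "follows a known or expected response pattern to the suspected intervention, that could not be reasonably explained by the known characteristics".
- **Not Related** applies when the event has some other etiology, with underlying disease among the examples, and/or when the timing is implausible.

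The section presents this as a general guideline, meant to make causality assessments consistent. An event recorded without an assessment is pursued until one is assigned.

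Other sections set the causality bar differently. For a SUSAR, 9.1.3 asks whether "there is a certain degree of probability that the event is a reaction to the study drug being researched". For serious events arising after participation, 9.4 says those "considered by the Investigator to be possibly related to study drug must also be reported".

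Section 2.3 lists what monitoring is meant to catch: "early signs of macular edema appearance or worsening, decrease in BCVA, the elevation of IOP, intraocular inflammation, lens opacities, and retinal structural modifications". In the analysis section, 10.8.1 says that "relationship to study drug will also be tabulated".

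**The concern.** A causality definition should capture suspected drug reactions, including kinds not seen before. Requiring a known or expected pattern puts expectedness inside relatedness, although 9.1.3 treats the two as separate tests. Requiring that the subject's clinical state could not reasonably explain the event sets a high bar in a progressive retinal disease, where possible drug harm and disease progression can look alike.

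This matters here because the study is open-label with no placebo, so there is no concurrent control arm against which to check attribution. Prior experience is also thin: Section 2.5 describes single doses in the first-in-human study and data from 20 subjects, whereas this extension repeats dosing and can treat both eyes.

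Four things depend on the recorded answer:

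- 9.3.1 continues follow-up past the end-of-study visit only for SAEs related to treatment.
- 9.4 requires an immediate telephone report for fatal or life-threatening events that the investigator attributes to the drug.
- 4.2.2.1 feeds related events into the subject's benefit-risk assessment.
- 10.8.1 tabulates by relationship.

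**Working it through.** There is no planned figure to reproduce. The study is not powered (10.2: "The sample size is determined by the number of subjects completing preceding QR-421a studies"), and the point concerns wording, so the check is to run types of event through the definitions.

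**Step 1: how the elements combine.** The bracket has three elements: (a) reasonable timing, (b) a known or expected response pattern, (c) no reasonable explanation from the subject's clinical state. They follow 'i.e.', are separated by commas and have no 'or'. The natural reading is (a) and (b) and (c). Not Related is joined by 'and/or', so either limb is enough.

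**Step 2: apply both definitions to well-timed events.**

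| Event | (a) | (b) | (c) | Related? | Not Related? |
|---|---|---|---|---|---|
| Known pattern, no other explanation | met | met | met | yes | no |
| Novel pattern, no other cause | met | fails | met | no | no: timing is plausible and there is no other etiology |
| Known pattern, disease could also explain it | met | met | fails | no | steered there, since underlying disease is a named etiology |

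The second row has no category. Because an unassigned event is chased until causality is entered, the investigator must choose one answer that does not fit.

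**Step 3: which monitored events fall in the third row.** Section 2.3 names six items. Sections 2.1 and 2.3 describe RP as photoreceptor degeneration with progressive vision loss ending in blindness. From the documents alone, two of the six can readily overlap with the disease: decrease in BCVA and retinal structural modification. Macular edema is not counted, because neither document says that RP causes it; Section 5.3.2 mentions it only as an eligibility matter.

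**Step 4: compare thresholds.** The 9.1.3 wording asks for some probability of a drug reaction and does not require other causes to be excluded. The 9.4 wording asks only for a possible relation. Events in the second and third rows could meet both and still fail 9.2.2.

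**Step 5: direction.** Compared with a reasonable-possibility test, elements (b) and (c) can only remove events from Related; neither adds any. Any effect on recorded relatedness is therefore downward. The documents give no event counts or misclassification rates, so its size cannot be derived.

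**The case against.** The strongest reply is that 9.2.2 is guidance. Its head definition is simply an event related to the drug or its administration, and the bracket is a gloss. Element (c) is a judgement about one subject, not about whether RP can ever cause such an event. Not Related calls for an actual other etiology, not a conceivable one. A sensible investigator could still record a novel reaction as Related.

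There are also safeguards. Section 9.4 sends every SAE to the sponsor within 24 hours whatever the suspected cause, with a causality rationale. The primary endpoints in 4.1.1 are incidence and severity of ocular and non-ocular events irrespective of relatedness, and 10.1 counts all adverse events toward the safety profile. The AE tables named in SAP 5.6 include none by relationship, although the output shells are in a separate document.

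All of this stands and limits the point. It does not remove it. The guideline exists to make assessments consistent and no other section overrides it. The 24-hour rule does not correct the recorded causality, and it does not cover non-serious events.

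A reader might infer more than the documents support:

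- *That such events can never be recorded as Related.* A general guideline is not an absolute bar.
- *That Related and unexpected nearly exclude each other, so a SUSAR could hardly arise.* Expectedness in 9.1.3 is judged against the reference safety information. A reaction may follow a known pattern and still be unlisted there.
- *That the 9.1.3 phrase "the nature and severity of the reaction are not in agreement with the product information" disables the severity test because it says 'and'.* The same sentence explains itself as meaning unexpected per the reference safety information.
- *That the shortfall can be put as a number.* Assuming some true cases and then assuming all are misclassified returns only the assumption.

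**Conclusion.** The concern holds as a defect of wording. Applied as written, 9.2.2 gives a well-timed novel reaction no category, moves events the disease could also explain toward Not Related, and sets a stricter bar than 9.1.3 and 9.4. This can bias recorded relatedness downward by an amount the documents do not allow anyone to estimate.

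The conclusion assumes that the three elements are read together and that investigators follow the guideline literally; looser use would shrink the effect. The consequences are confined to the four uses of the classification listed above. The primary endpoints are unaffected. The effect on reported tables depends on whether any output is produced by relationship, because SAP Section 6 limits reporting after the early stop to summary tables and listings. The point is worth correcting, but it does not undermine the safety analysis as a whole.

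**What to change.** Replace the bracket under Related in 9.2.2 with:

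> there is a reasonable possibility that the study drug caused the event; a known response pattern supports this but is not required, and a possible alternative cause such as the underlying disease does not by itself make the event Not Related

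Use this single threshold in 9.1.3, 9.4 and the 10.8.1 tabulation. Keep expectedness as a separate question, judged against the reference safety information as 9.1.3 already provides.

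Because the sponsor stopped the study early, new wording would come too late for most data. For events already recorded, either re-review causality, giving priority to those the disease could also explain and those of a new kind, or state in the clinical study report that the definition may have lowered recorded relatedness.

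The cost is a few words of protocol text and a note to sites, or a limited re-review. The downside is that somewhat more events will be classed as related and will need review.
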